4.3 Subject Recruitment and Screening

Study subjects will be recruited from the Dartmouth Hitchcock Department of Surgery, Division of Colon and Rectal Surgery clinical practice. Patients will be deemed eligible for the study based upon clinical indicators for appropriateness of ileostomy closure.

4.4 Early Withdrawal of Subjects

4.4.1 When and How to Withdraw Subjects

Patients may be withdrawn from the study at any time based upon withdraw of consent. Patients may also be withdrawn if the study treatment cannot be tolerated (i.e. removal of mesh device is required). Patients must continue to participate for 30days post-operatively in order for inclusion in the analysis of the primary endpoint data.

4.4.2 Data Collection and Follow-up for Withdrawn Subjects

Data related to the time period of the subject's participation will be included in the analysis of the treatment effect. Should a subject be withdrawn from the study for any reason, survival data will be maintained in accordance with the guidelines for follow-up prescribed by the NCCN.

5 Study Procedures

5.1 Encounter 1

Patients will be assessed for ileostomy closure based upon completion of therapy after primary resection of their malignancy. Appropriate candidates will be determined at the operating surgeon's discretion based on customary evaluation of clinical status. The informed consent process will be initiated and the patient recruited into the study.

5.2 Encounter 2

This encounter is the operative procedure. The procedure for closing the ileostomy (i.e. bowel anastomosis) will be at the discretion of the surgeon, provided it is performed through the ileostomy site without additional laparotomy incisions. In accordance with SCIP guidelines, pre-operative intravenous antibiotic and subcutaneous pharmacologic venous thromboembolism prophylaxis will be administered. Patients with a history of MRSA infection will also receive a dose of intravenous vancomycin prior to the procedure.

The abdominal wall reconstruction portion of the procedure will be standardized to ensure consistency between surgeons. The posterior rectus sheath is closed with native tissue either primarily, using hernia sac if present, or bridged with Vicryl-type mesh and a quickly absorbing suture material. This is done to isolate the mesh from the peritoneal cavity. The retrorectus plane is developed using electrocautery and blunt dissection to provide adequate placement of mesh such that it overlaps the posterior sheath defect by a minimum of 3cm on all sides. The mesh is placed in this plane and secured in place with slowly absorbable monofilament (0-PDS preferred) sutures placed through the anterior fascia or with application of fibrin sealant at the surgeon's discretion. This space is then irrigated with

250mL of bacitracin/neomycin/polymixin antibiotic solution, patients with a history of MRSA will have vancomycin added to this solution. The anterior rectus sheath is then closed in a running fashion with slowly absorbing monofilament suture (0-PDS preferred). Again, 250mL of antibiotic solution are used as irrigation. A closed suction drain may be left in the retrorectus space at the discretion of the surgeon. Scarpa's layer is closed if possible and then skin closed with a circumferential purse string absorbable suture and the subcutaneous cavity packed with Iodoform gauze. This gauze is then removed on post-operative day 2. Post operatively the patient will receive standard care.

5.3 Encounter 3, 4, 5, et al.

The patients will be seen at 30days following discharge from hospitalization for stoma closure for a clinical examination and then will undergo standard follow-up for their cancer surveillance in accordance with NCCN guidelines which include computed tomography imaging every 6 months. Concurrently, clinical cancer surveillance evaluation by the operating surgeon (in conjunction with surveillance visits by medical oncology) will be performed on the same schedule with evaluation of clinical evidence of hernia formation as well as assessment of patient experience with the stoma site as part of regular cancer surveillance visit. These images will be subsequently evaluated for radiographic evidence of hernia formation by a radiologist blinded to the presence of the mesh, which is radiolucent. Patients will be undergoing computed tomography evaluation primarily as part of their cancer surveillance, and this imaging is not obtained expressly for the purposes of this study, and are only secondarily utilized to screen for hernia occurrence. Patients will also undergo ultrasound examination of the ostomy closure site at 30d post operatively then on the same 6 month schedule. These images are obtained for the purposes of the study and are intended to be compared to the computed tomography findings to evaluate congruence of the two modalities. These visits occur on a prescribed schedule for a period of 5 years after cancer treatment has concluded, after which no further follow-up is required.

Sonographic evaluation of the stoma site will be obtained on the Supersonic Unit in the Advanced Imaging Center using an 8-15 mHz linear transducer.

Cine clips will include all margins of the mesh repair to ensure adequate coverage of the repair site.

SUPINE:

Patients will initially be examined in the supine position.

1. Longitudinal and Transverse images of the stoma site will be obtained with normal breathing followed by a video clip in long or transverse plane.
2. Longitudinal and Transverse images of the stoma site will be obtained with Valsalva maneuver followed by a video clip in long or transverse plane with Valsalva.
3. If a stoma site hernia is identified, measurements of the abdominal wall defect will be obtained with and without Valsalva.
4. If a stoma site hernia is identified Longitudinal and Transverse images of the stoma site will be obtained with transducer compression followed by a video clip in long or transverse plane.

STANDING:

Patients will then be examined in the standing position.

- 1) Longitudinal and Transverse images of the stoma site will be obtained with normal breathing followed by a video clip in long or transverse plane.
- 2) Longitudinal and Transverse images of the stoma site will be obtained with transducer compression followed by a video clip in long or transverse plane.
- 3) If a stoma site hernia is identified on standing views only, measurements of the abdominal wall defect will be obtained with and without Valsalva.

- 4) If a stoma site hernia is identified on standing views only, Longitudinal and Transverse images of the stoma site will be obtained with transducer compression followed by a video clip in long or transverse plane.

6 Statistical Plan

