3.3 Secondary Study Endpoints

The secondary endpoints will be evaluation of the incidence of hernia formation at the ileostomy site on a prospective basis at 30 days and 6 month intervals thereafter until two years from the date of ileostomy closure. The Promis SF 2.0 8a Ability to Participate in Social Roles and Activities instrument will be used to assess quality of life and the Colorectal Functional Outcome (COREFO) instrument will be used to evaluate bowel function at each interval.

4 Subject Selection and Withdrawal

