6.4 Subject Population(s) for Analysis

The statistical analysis for this study will use an all-treated population: Any subject who participated in the study and underwent the study procedure. Patients without complete follow-up data will be excluded from the final analysis.

7 Safety and Adverse Device Effects

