At screening, any clinically significant abnormality should be recorded as a preexisting condition. At the end of the study, any new clinically significant findings/abnormalities that meet the definition of an adverse event must also be recorded and documented as an adverse event.

Post-study Adverse Event

All unresolved adverse events should be followed by the investigator until the events are resolved, the subject is lost to follow-up, or the adverse event is otherwise explained. At the last scheduled visit, the investigator should instruct each subject to report any subsequent event(s) that the subject, or the subject's personal physician, believes might reasonably be related to participation in this study. The investigator should notify the study sponsor of any death or adverse event occurring at any time after a subject has discontinued or terminated study participation that may reasonably be related to this study. The sponsor should also be notified if the investigator should become aware of the development of cancer or of a congenital anomaly in a subsequently conceived offspring of a subject that has participated in this study.

Abnormal Laboratory Values

A clinical laboratory abnormality should be documented as an adverse event if any one of the following conditions is met:

- The laboratory abnormality is not otherwise refuted by a repeat test to confirm the abnormality
- The abnormality suggests a disease and/or organ toxicity
- The abnormality is of a degree that requires active management; e.g. change of dose, discontinuation of the drug, more frequent follow-up assessments, further diagnostic investigation, etc.

Hospitalization, Prolonged Hospitalization or Surgery

Any adverse event that results in hospitalization or prolonged hospitalization should be documented and reported as a serious adverse event unless specifically instructed otherwise in this protocol. Any condition responsible for surgery should be documented as an adverse event if the condition meets the criteria for and adverse event.

Neither the condition, hospitalization, prolonged hospitalization, nor surgery are reported as an adverse event in the following circumstances:

- Hospitalization or prolonged hospitalization for diagnostic or elective surgical procedures for a preexisting condition. Surgery should **not** be reported as an outcome of an adverse event if the purpose of the surgery was elective or diagnostic and the outcome was uneventful.

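### Mesh removal can end hernia follow-up, and section 6.4 can then drop the patient, so the two-year hernia incidence may be biased, plausibly downward but by little

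*Combined protocol and SAP*

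**What the plan says.** Four sections bear on this.

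- **Withdrawal (4.4.1).** Besides withdrawal of consent: "Patients may also be withdrawn if the study treatment cannot be tolerated (i.e. removal of mesh device is required". The wording is permissive.
- **Data after withdrawal (4.4.2).** "Should a subject be withdrawn from the study for any reason, survival data will be maintained", following NCCN follow-up guidelines. Survival is the only item named, and it is not an endpoint in 3.2 or 3.3. The same section keeps what was gathered earlier: "Data related to the time period of the subject's participation will be included in the analysis of the treatment effect".
- **Hernia endpoint (3.3).** The secondary endpoint is hernia incidence at the ileostomy site, "at 30 days and 6 month intervals thereafter until two years from the date of ileostomy closure". PROMIS and COREFO are collected at the same intervals.
- **Analysis population (6.4).** The population is all treated patients, but "Patients without complete follow-up data will be excluded from the final analysis".

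Section 5.3 adds that CT and the surgeon's examination for hernia are part of regular cancer surveillance. Of the CT it says "this imaging is not obtained expressly for the purposes of this study". Ultrasound, in contrast, is done for the study. Nothing provides for hernia assessment, or for study reading of routine CT, after a patient is withdrawn.

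**The concern.** Losing the device and leaving the study are different events, and these sections let the first lead to the second. Removing the mesh is a failure of the intervention: 3.2 lists its excision among the wound interventions of particular interest. If the same event can end hernia follow-up, missing hernia data are tied to treatment failure.

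The Background (1.1) argues that mesh lowers the failure rate of repair. On that premise, patients who lose the mesh are at higher risk of hernia than those who keep it, and leaving them out would tend to make the reported incidence look better.

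Sections 4.4.2 and 6.4 also do not fit together. The first keeps data from the period of participation. The second can exclude the whole patient, including a hernia found before withdrawal. The exclusion in 6.4 is what removes the patient from the denominator.

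The pilot is meant to inform a randomized trial. If the rule were carried into that trial, only the mesh arm could trigger it, and the loss would differ between arms.

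**Working it through.** **The plan's own figure.** The plan gives no estimator, missing-data method or expected hernia rate for the pilot. Its only related figure is the sample size (6.2): 10% × 200 = 20, which agrees with 5 + 15 in the two-phase design (3.1). N = 20 is used below.

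**Inputs.**
- Mesh removal rate m = 4% (1.3.1, from the cited multi-institution mesh study).
- Hernia rate without reinforcement: about 1/3 (1.1).
- Hernia rate with mesh kept, h_keep = 1/6: the 50% reduction hypothesized for the later study (6.3) applied to 1/3. This is an assumption for the pilot.
- Hernia rate after mesh removal, h_rem: not given anywhere. Range assumed: 1/6 (no different), 1/3, 43% (the upper recurrence figure for primary hernia repair in 1.1, used as a proxy) and 100%.

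**Step 1: how often removal would arise.**
- Expected removals: 20 × 0.04 = 0.8.
- P(at least one) = 1 − 0.96^20 = 55.8%.
- P(at least two) = 19.0%.

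**Step 2: expected understatement.** Suppose every patient whose mesh is removed is withdrawn and excluded. The analysis then estimates h_keep, while the all-treated incidence is (1 − m) × h_keep + m × h_rem. The difference is m × (h_rem − h_keep).

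| h_rem (assumed) | All-treated incidence, m = 4% | Reported | Understatement, m = 4% | Understatement, m = 10% (assumed) |
|---|---|---|---|---|
| 1/6 | 16.7% | 16.7% | 0 | 0 |
| 1/3 | 17.3% | 16.7% | 0.7 points | 1.7 points |
| 43% | 17.7% | 16.7% | 1.1 points | 2.6 points |
| 100% | 20.0% | 16.7% | 3.3 points | 8.3 points |

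For example, 0.04 × (0.43 − 0.1667) = 0.0105.

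**Step 3: one lost patient in whole numbers.** With 3 hernias among the 19 who remain, the report is 3/19 = 15.8%. The all-treated figure is 3/20 = 15.0% if the lost patient has no hernia and 4/20 = 20.0% if there is one. In a single sample the error can go either way.

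**Step 4: against sampling error.** The exact 95% interval for 3/20 is 3.2% to 37.9%.

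**Step 5: losses from any cause.** Section 2 aims for retention above 80%. At 80%, four patients are lost. With 3 hernias among 16, the report is 3/16 = 18.8%, and the all-treated bounds are 3/20 = 15.0% to 7/20 = 35.0%.

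**The case against.** The case on the other side has several parts.

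- **Withdrawal is discretionary.** The 56% is the chance of a removal, not of a lost hernia outcome. This stands; the figures in step 2 assume every removal leads to withdrawal and exclusion.
- **The direction is not established.** No document gives a hernia rate after mesh removal, and withdrawal of consent has no known direction. This stands. A reader might infer that the incidence is certain to be too low; the documents make that plausible and no more.
- **The 4% comes from another setting**, contaminated ventral hernia repair. In addition, 7.4 suspends the trial when a return to the operating room requires mesh removal, so several removals are unlikely to accumulate without review. Both stand and weaken any scenario with two or more removals.
- **Safety follow-up continues.** A reader might infer that 4.4.2 contradicts 7.1, where "All unresolved adverse events should be followed by the investigator until the events are resolved". It does not: 4.4.2 concerns outcome data. Sections 7.1 and 7.2 concern safety and would still capture many later wound re-interventions. They do not supply scheduled hernia assessment.
- **There is no hernia threshold to cross.** A reader might infer that lost patients could move the pilot across a target of 16.7%. The 50% reduction in 6.3 is a hypothesis for the later study, and the pilot has no hernia decision rule.
- **The information may still exist.** Surveillance CT and surgeon visits are routine care, so hernia status is uncollected rather than unobtainable. This stands, and it is why the remedy is cheap.

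What remains is that no section provides for hernia status after withdrawal, and 6.4 can exclude the patient.

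**Conclusion.** The point holds in a limited form. Read together, 4.4.1, 4.4.2 and 6.4 allow two-year hernia status to be lost for a reason tied to device failure, so the reported incidence may be biased. Downward is the plausible direction on the protocol's own premise about mesh.

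The expected size at 4% removal is about 0.7 to 1.1 points, with 3.3 points at the extreme. That rests on h_keep = 1/6, on the assumed hernia rates after removal, and on every removal ending in exclusion. If removed patients herniate no more than the rest, the expected bias is zero. At N = 20 the effect is minor beside sampling error. The reason to correct it is that the rule is wrong in principle, inexpensive to mend, and could pass into the randomized trial.

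A reader might also infer that a mesh removal would count against the retention target. Retention is not defined, so the documents do not settle this.

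**What to change.** - **4.4.1:** separate mesh removal from withdrawal from study follow-up, and record it as an outcome. This concerns data collection only; decisions about the mesh itself are unaffected.
- **4.4.2:** with the patient's consent, and within the limits of 8.1 where authorization is revoked, continue to collect through two years: hernia status from routine surveillance CT and surgeon examination, wound re-interventions, and vital status.
- **6.4:** amend the exclusion of incomplete follow-up so that these patients stay in the all-treated denominator, and reconcile it with 4.4.2. Without this change the first two would have no effect on the analysis.
- **Reporting:** give hernia incidence in all implanted patients, whether or not the mesh is still in place. For any patient whose status is unknown, give best- and worst-case bounds as in step 5.

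The cost is protocol and consent wording, some extra data abstraction, and reading of CT already obtained for surveillance. The hernia rate may look less favourable. No added imaging is needed for the CT and clinic data. Study ultrasound and questionnaires after mesh removal would add study procedures, so they can be optional.

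### In section 5.3 the standing ultrasound list has no routine Valsalva view and asks for compression twice, so it does not match the supine list

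*Combined protocol and SAP*

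**What the plan says.** Section 5.3 (Encounter 3, 4, 5, et al.) sets out two numbered ultrasound lists, one supine and one standing.

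Supine, every patient has a normal-breathing acquisition and then a straining one: "2. Longitudinal and Transverse images of the stoma site will be obtained with Valsalva maneuver". The clip in that step is also taken with Valsalva. Compression comes last and is conditional: "4. If a stoma site hernia is identified Longitudinal and Transverse images of the stoma site will be obtained with transducer compression".

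Standing, every patient again starts with normal breathing, but the second routine step is "2) Longitudinal and Transverse images of the stoma site will be obtained with transducer compression". Valsalva first appears in step 3, which is conditional: "3) If a stoma site hernia is identified on standing views only, measurements of the abdominal wall defect will be obtained with and without Valsalva". Step 4, under the same condition, asks for compression images and a clip.

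The same section says that these scans are done for the study, at 30 days and then on the 6-month schedule, and are to be compared with CT for congruence. Section 3.3 makes hernia incidence at the stoma site a secondary endpoint. Section 2 makes evaluation of the hernia-monitoring process part of Secondary Objective #2.

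**The concern.** The condition in standing steps 3 and 4 refers to hernias seen on standing views only. The standing examination is therefore expected to pick up hernias that the supine views, including supine Valsalva, did not show. Yet on the standing list the straining manoeuvre is never used for detection, only for measurement once a hernia is already known. A hernia that appears only with standing and straining together would not be looked for on the study ultrasound.

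The list also asks for the same compression acquisition twice, once in everyone and once if a hernia is found. An operator could reasonably follow the text, or could assume that the supine order was meant. Scans could then differ between patients or visits in a way the protocol does not record.

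At stake are the hernia data that section 6.3 expects to inform a larger trial, and an imaging procedure that the pilot is meant to try out. Correcting it costs very little.

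**Working it through.** The plan gives no figure on this point to reproduce. The check is a line-by-line comparison of the two lists in section 5.3.

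| Step | Supine | Standing |
|---|---|---|
| 1 | Normal breathing, everyone | Normal breathing, everyone |
| 2 | Valsalva, clip with Valsalva, everyone | Compression and clip, everyone |
| 3 | If hernia: measure with and without Valsalva | If hernia on standing views only: measure with and without Valsalva |
| 4 | If hernia: compression and clip | If hernia on standing views only: compression and clip |

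1. **Match.** Steps 1, 3 and 4 correspond, apart from the standing-only qualifier in steps 3 and 4. Step 2 is the only step whose manoeuvre differs.

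2. **Duplication.** Standing steps 2 and 4 describe the same acquisition. Any patient who meets the step 4 condition has already had it in step 2, so step 4 as worded adds nothing new.

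3. **Gap.** The unconditional views are supine at rest, supine with Valsalva, standing at rest and standing with compression. Standing with Valsalva is the combination left out. No other section supplies it or explains its absence. Standing step 3 uses Valsalva for measurement, so the protocol already treats it as feasible in that position.

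4. **What else could find such a hernia.** Section 5.3 gives every patient the supine Valsalva views, CT every 6 months read by a radiologist blinded to the mesh, clinical evaluation by the operating surgeon, and repeat ultrasound. The exposure is to hernias seen only with standing and straining combined. To be lost from the study altogether, they would also have to escape these other assessments.

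5. **Scale only.** With 20 patients (section 6, sample size), one patient moves an observed proportion by 1/20 = 5 percentage points. As an illustration, take the background rate of one third (section 1.1), giving 20 × 1/3 = 6.67 expected hernias, and suppose that ultrasound alone decided the endpoint. Assumed miss fractions of 10%, 20% and 30% would give 6.67 × 0.9 / 20 = 30.0%, 6.67 × 0.8 / 20 = 26.7% and 6.67 × 0.7 / 20 = 23.3%. The miss fractions are assumptions with no source in the documents, so these are not estimates.

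6. **Cost of the change, in standing image sets per examination.** With no hernia, the current list takes 2 (steps 1 and 2). Replacing compression with Valsalva in step 2 keeps 2; adding Valsalva as a separate step makes 3. With a standing-only hernia, the current list takes 3 (steps 1, 2 and 4), and either remedy also gives 3. The most that is added is one.

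**The case against.** The strongest case against is that this is a small difference in technique with several safeguards around it.

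- **Standing is itself a challenge to the abdominal wall.** The standing-only condition shows that the authors expect posture alone to reveal some hernias. A reader might infer that the standing examination is less provocative overall than the supine one. The documents never compare standing posture with supine Valsalva, so that stands only for the listed manoeuvres.
- **Detection is layered.** This stands, and it limits the consequence. It does not remove the gap in the ultrasound itself, which is the examination done solely for the study.
- **Ultrasound may not decide incidence.** Section 3.3 names no deciding modality, and section 5.3 gives the ultrasound's purpose as comparison with CT. A reader might infer that reported incidence is biased downward. That would follow only if ultrasound findings count towards the endpoint and the other assessments miss the same hernias.
- **The CT comparison.** A reader might infer that it is confounded. The documents give no CT position or breathing instruction, so whether a standing Valsalva view would raise or lower congruence is unknown.
- **The duplication loses no data.** True: step 4 may be meant to capture images of the hernia just identified. A copying slip is a natural reading, because the supine list has Valsalva in that slot, but the documents do not establish it. Routine standing compression may be deliberate, and the remedy has to allow for that.

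**Conclusion.** The mismatch is real and worth correcting. The standing list has no routine Valsalva acquisition, and its step 2 repeats conditional step 4. Hernias visible only with standing and straining together could go undetected on the study ultrasound. This follows from the text of section 5.3 alone and assumes only that operators follow the list as written.

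Its effect cannot be sized from the documents. A reader might infer a 15% to 30% relative understatement of incidence, from one missed hernia among 6.67 expected (1/6.67 = 15%) or among 3.33 if the 50% reduction hypothesised in section 6.3 held (1/3.33 = 30%). That range presumes exactly one miss. It reflects how small a cohort of 20 is and does not measure what the missing view would cost.

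The point bears on the secondary hernia endpoint and the ultrasound-CT congruence comparison. It does not touch the 30-day primary endpoint, the two-stage rule or the sample size.

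**What to change.** Reconcile the two lists in section 5.3, in one of two ways.

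- **If standing step 2 was meant to mirror supine step 2:** make it a routine Valsalva acquisition in every patient, and state that the clip is also taken with Valsalva. Changing only the words for the still images would leave the clip unspecified. Compression then stays in conditional step 4.
- **If routine standing compression was intended:** keep it, add the Valsalva images and clip as a separate unconditional step, and delete the duplicate step 4.

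Either is a short edit to the protocol text. The downside is at most one extra short acquisition within an examination already being done, with no added visit or staff.
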